10.0 Removal of Subjects from Protocol Therapy

10.1 Duration of Treatment

Subjects will continue vandetanib or placebo up to and including the morning of surgery for a total of 7 to 14 days. The time frame from preoperative clinic visit until definitive surgery will be a minimum of 2 weeks and the maximum of 4 weeks. Subjects with an adverse reaction of CTCAE grade III or higher will discontinue the study drug. Subjects can voluntarily discontinue the drug at any time during the trial, be removed from the drug at the discretion of their treating physician, or be discontinued by the study investigators. In previous trials with vandetanib, surveillance labs and toxicity assessment has been performed at two weeks of treatment, which will be done in this trial with the preoperative safety assessment. Because subjects will have already discontinued the study drug at that time it will not be possible to discontinue the study drug early based on that assessment. Due to the short duration of treatment in this trial and the low incidence of adverse reactions over that time frame in previous phase I and II trials we do not expect a significant number of severe adverse reactions. Subjects will be evaluated for study withdrawal if noncompliant with requirement for therapy, or if they are experiencing drug related toxicity. If the date of surgery is unexpectedly changed after initiation of treatment, the patient will continue treatment, including the morning of surgery, for not more than 28 total days.

10.2 Extraordinary Medical Circumstances:

If at any time the constraints of this protocol are detrimental to the subject's health and/or the subject no longer wishes to continue protocol therapy, remove the subject from the protocol treatment. In this event:

- Document the reason(s) for ending treatment on the follow-up form.
- The primary outcomes of response of down regulation of Ki-67 and secondary outcomes of evaluation of tumor markers in the baseline and endpoint tissue samples will be analyzed unless the subject withdraws consent to do so.

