6.0 Treatment Plan

Subjects meeting the eligibility requirements in Section 4.1 and who have given signed informed consent will start the treatment dose of Vandetanib 300 mg or placebo orally, daily, starting such time as to allow 7 to 14 doses with the 7th or 14th dose given on the morning of the operation. Patients will return to clinic the day before the scheduled operation or the morning of surgery for repeat laboratory studies and EKG. Costs of the post-treatment labs and EKG will be covered by the PI. The results will be reviewed and safety to proceed documented prior to the operation. The study calendar (which will be provided at the pretreatment office visit to document administration of the study drug and any side effects associated with treatment) will be reviewed, pill counts performed, and an adverse events assessment performed at that time. Any concerns related to toxicities and safety to proceed to surgery will be addressed with the attending surgeon at that time. Common induction anesthetics (isoflurane, desflurane and sevoflurane) can cause QTc prolongation. Any QTc (>440 ms) on EKG should be discussed with the attending anesthesiologist prior to induction, and these induction agents should not be used if QTc > 480 ms. A flow chart of the preoperative screening procedure is shown in appendix 3. Subjects will be instructed to take their medication at the same time each day. In general subjects should take their dose every day even if it is not at the recommended time. Specific questions regarding timing and doses can be directed to [name] [contact], [name]). Patients will be removed from the study for failure to take at least 80% of the study doses. Patients will not be replaced if they are removed from the trial.

Women of Childbearing Potential (WOCBP) must use *highly effective* methods of birth control (one method or a combination of methods that results in a less than 1% failure rate per year) throughout therapy and must maintain full contraception for at least 95 days after the last dose of Vandetanib.

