The first dose of Vandetanib tablets will be taken only after all the assessments assigned have been performed. Patients should take study drug in the morning. If a patient inadvertently misses a dose and the next dose is in 12 hours or more, the patient should take the missed dose immediately and the next dose at the normal time. If it is less than 12 hours before the next dose, the patient should take the next dose at the normal time and the missed dose should not be taken. The missed dose must be documented in the CRF, where appropriate, with a comment indicating the patient missed the dose. The dose of study treatment may be repeated if vomiting occurs within 30 minutes of taking the study treatment. If vomiting occurs after 30 minutes of taking the study treatment, the dose will not be repeated.

Labels will be prepared in accordance with Good Manufacturing Practice (GMP) and local regulatory guidelines. The labels will fulfill GMP Annex 13 requirements for labeling.

Information on the bottle labels for Vandetanib will indicate the study number, contents, caution, and storage conditions and will have blank spaces for the patient number, visit number, and dispensing date (to be written in by the site personnel at the center at the time of dispensing). Instruction that study drug should be taken as directed will be included on the label. Patients will be supplied with a study participation card where the dosing instruction will be described for a patient by Investigator or delegate. All study drugs should be kept in a secure place under appropriate storage conditions

Administration

Subjects will be asked to take Vandetanib as a single oral daily dose of 300 mg or placebo. Patients will discontinue the drug and be removed from the study for toxicity. A patient may withdraw from the study at any time for any reason without prejudice for future treatment. Patients will be removed from the study for failure to comply with greater than 80% of scheduled doses.

Toxicity

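### Section 10.1 says the drug is already stopped at the preoperative safety visit, but a dose can still be due; the visit heading and the 80% rule also conflict between sections

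*Combined protocol and SAP*

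**What the plan says.** **Last dose.** Section 10.1 opens: "Subjects will continue vandetanib or placebo up to and including the morning of surgery for a total of 7 to 14 days". Section 6.0 agrees on the morning of surgery: "starting such time as to allow 7 to 14 doses with the 7th or 14th dose given on the morning of the operation".

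**Safety visit.** Section 6.0: "Patients will return to clinic the day before the scheduled operation or the morning of surgery for repeat laboratory studies and EKG". It then adds: "The results will be reviewed and safety to proceed documented prior to the operation". The schedule in Section 5.0 labels the same visit as post-treatment and dates it Day 13 or 14.

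**Stopping on that visit.** Section 10.1, later in the same paragraph: "Because subjects will have already discontinued the study drug at that time it will not be possible to discontinue the study drug early". Section 11.2.3 requires drug to be withheld and the patient removed after a single QTc above 500 ms, with no exception for this visit.

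**Adherence.** Section 6.0: "Patients will be removed from the study for failure to take at least 80% of the study doses". Section 7.1, under Administration: "Patients will be removed from the study for failure to comply with greater than 80% of scheduled doses". The stopping rules in Appendix 5 use the Section 6.0 threshold.

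**The concern.** The sentence in Section 10.1 is wrong for visit timings that Section 6.0 allows. A patient seen the day before surgery, or that morning before the tablet, has not finished treatment. Section 6.0 asks for results to be reviewed before the operation, not before the dose. Staff who take Section 10.1 at its word have no prompt to hold the last tablet until the ECG is read, and could give a dose that Section 11.2.3 would withhold. Section 7.1 names QT prolongation and Torsades de pointes among the major toxicities, so this is the one place where the wording bears on safety.

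The other two conflicts are minor. A visit dated Day 13 or 14 cannot also be preoperative in the shorter courses. And two thresholds for removal can classify the same patient differently, in a trial where Section 6.0 says removed patients are not replaced.

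**Working it through.** There is no stated figure to reproduce. The check sets the sections against each other and counts.

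**Inputs.** Last dose on the morning of surgery (Sections 6.0 and 10.1). Visit on the day before or that morning (6.0). Planned course of 7 to 14 doses (6.0 and 10.1). Visit heading of Day 13 or 14 (5.0). Threshold of at least 80% (6.0, Appendix 5) or greater than 80% (7.1).

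**Doses left at the visit.** Let n be the number of daily doses, with none missed, the first on Day 1 and the last on Day n, the day of surgery.

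- Visit on Day n−1, before that morning's tablet: n − (n−2) = 2 left.
- Visit on Day n−1, after the tablet: n − (n−1) = 1 left.
- Visit on Day n, before the tablet: n − (n−1) = 1 left.
- Visit on Day n, after the tablet: n − n = 0 left.

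The Section 10.1 sentence is true only in the last case. The result does not depend on n.

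**Visit heading.** Day 13 comes after surgery whenever 13 > n, that is for n = 7, 8, 9, 10, 11 and 12. That is 6 of the 8 lengths from 7 to 14. Section 6.0 can also be read as allowing only 7 or 14 doses, because it names the 7th or 14th dose as the one taken on the morning of the operation. On that reading the heading fails for 7 and works for 14.

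**80% rule.** The two wordings differ only where 0.8 × n is a whole number.

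- n = 7: 0.8 × 7 = 5.6, so the minimum is 6 under both.
- n = 10: 0.8 × 10 = 8, so the minimum is 8 under one wording and 9 under the other.
- n = 14: 0.8 × 14 = 11.2, so the minimum is 12 under both.

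Within 7 to 14 doses only n = 10 differs, 1 length of 8. If only 7 or 14 doses were on plan, no planned course would be affected.

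**The case against.** The strongest reply is that the harm is small and largely controlled. Section 6.0 sends any QTc above 440 ms to the anaesthesiologist and rules out the listed induction agents above 480 ms. A reader might infer that a patient above 500 ms could go on to receive those agents; the protocol already forbids it. The Section 11.2.3 rule is mandatory, and Section 10.1 itself lets the treating physician or investigators stop the drug. The disputed sentence can be read as background rather than instruction. Appendix 3, which charts the preoperative procedure, is not shown and may set the order of ECG and dose. All of this limits the stake to the remaining study dose. It does not make the sentence true, and no flowchart can reconcile Section 10.1 with its own opening.

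On adherence, the difference bites only at exactly 80%, and Section 12 already enrolls 40 per arm for 35 evaluable. That stands, and is why this part is minor.

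A reader might also infer that when surgery is moved and dosing continues, "the patient will continue treatment, including the morning of surgery, for not more than 28 total days", such patients get only one ECG on treatment and run out of tablets after the stated two-week supply plus two doses. The documents do not establish either. Section 6.0 ties the ECG to the operation with no exception for a changed date, so it can be read to require another before the moved operation. Section 7.1 refers to each dispensing visit, which does not exclude resupply. An added ECG and blood draw for these patients would be a new procedure, and it is not proposed here.

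**Conclusion.** The conflict holds as a correction of wording with one safety consequence. At the preoperative visit usually one dose, and at most two, can remain, so early stopping is possible and the 500 ms rule applies. This rests on the visit timing in Section 6.0 and on daily dosing to the morning of surgery. Where the visit follows the last tablet, Section 10.1 is right.

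The number of patients affected cannot be derived: the documents do not say how often visits precede the last dose or how often QTc will exceed 500 ms. The visit heading is unworkable before surgery for 6 of 8 lengths, but this is a labelling fault, since Section 6.0 gives every patient a preoperative check. The 80% wordings disagree at 1 of 8 lengths. None of this changes the power figures in Section 12.

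**What to change.** 1. **Sections 10.1 and 6.0.** Delete the sentence in 10.1 that rules out early discontinuation. In 6.0, require the preoperative ECG to be read before the last dose, and that dose to be withheld if QTc exceeds 500 ms. This applies the existing 11.2.3 rule at this visit. If Appendix 3 already gives this order, a cross-reference is enough.
2. **Sections 5.0 and 6.0.** Date the safety visit column by the operation (day before, or morning of surgery) in place of Day 13 or 14. In 6.0, state that any number of daily doses from 7 to 14 is on plan, the last on the morning of surgery.
3. **Section 7.1, Administration.** Set the threshold at no less than 80% of scheduled doses, matching 6.0 and Appendix 5.

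**Cost.** Edits to four sections and no new test or visit. Patients seen on the morning of surgery must be told to wait for the ECG before taking the tablet, which may delay that dose a little beyond the usual time. When the ECG is read on the day before, the surgery-morning dose need not be delayed.

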11.0 Data Management, Quality Control and Data Security

Data management for the optimal entry, processing, storage, and retrieval for this protocol's data will be accomplished by the PI. The data base will be located on a computer or in a locked cabinet in a locked office. This computer will be secured, accessible only by the research team. There will be more than one copy of the database. The second, secured, copy of the protocol data will be stored in a locked room accessible only by the research team. For quality control, auditing, and checking data for integrity, there will be a regular accounting date periodically performed.

11.1 Data and safety monitoring

- 1.1.1. **Purpose:** The Data Safety Monitoring Plan for this study (see Appendix 5) is written to ensure the safety of subjects and to verify the validity and integrity of the data.
- 1.1.2. **Assessment of risk:** This investigation involves risk-level 3 out of 4 (see appendix 5) procedures, in a population that is at risk of death or severe morbidity because of existing illness or disease.
- 1.1.3. **DSMC audits:** The CRSO will perform biannual audits of the research charts, case report forms and the corresponding primary source documents. Safety audits will be conducted to validate eligibility of patients accrued to study, check for the presence of informed consent, determine compliance with protocol, determine whether AE/SAE are being reported to internal and external regulatory agencies, and compare veracity of data in the research record with the primary source documents. As part of the ongoing monitoring of this study, the PI will maintain an AE summary table to be reviewed during the audits.

The results of each audit will be reviewed by the DSMC Chair and/or the study monitor. A final report for the audit will be sent to the PI, PRMC Chair, and the IRB, along with any resulting recommendations or required actions.

- 1.1.4. **Expedited reports:** All expedited adverse event reports will be reviewed by the DSMC.
- 1.1.5. **Continuing reviews:** All DSMC audit reports must be attached to continuing review submissions for the IRB approval.

11.2 Adverse Event (AE and Serious Adverse Event [SAE])

11.2.1 Definitions

An **adverse event** (AE) is defined in the *CTEP, NCI Guidelines* [2005] as “any unfavorable and unintended sign (including an abnormal laboratory finding), symptom or disease temporally associated with the use of a medical treatment or procedure (attribution of unrelated, unlikely, possible, probably or definite).”

A **serious adverse event** (experience) or reaction is any untoward medical occurrence that at any dose: results in death, is life-threatening, requires inpatient hospitalization or prolongation of existing hospitalization, results in persistent or significant disability / incapacity, or is a congenital anomaly / birth defect. Hospitalization for planned surgical treatment of breast cancer does not constitute an SAE.

The definition of serious adverse event (experience) also includes *important medical event*. Medical and scientific judgment should be exercised in deciding whether expedited reporting is appropriate in other situations, such as important medical events that may not be immediately life-threatening or result in death or hospitalization but may jeopardize the subject or may require intervention to prevent one of the other outcomes listed in the definition above. These should also usually be considered serious. Examples of such events are intensive treatment in an emergency room or at home for allergic bronchospasm; blood dyscrasias or convulsions that do not result in hospitalization; or development of drug dependency or drug abuse.

The definition of “**related**” is that there is a reasonable possibility that the drug caused the adverse experience.

Investigators are required by Federal regulations to report serious adverse events as defined in the tables below. If a subject has a reportable serious adverse event, the Study Chair and the Institutional Review Board follow guidelines of this table. This study will utilize the Common Toxicity Criteria version 4.0 to determine the severity of the reaction for adverse event reporting.

11.2.2 Assessment of Risk Level

The Data Safety Monitoring Plan (DSMP) can be found in Appendix 5 of this protocol.

This investigation involves a risk-level 3 procedure, in a population that should not be at any increased risk for complications.

11.2.3 Assessing Toxicity:

Toxicity will be graded according to NCI’s Common Toxicity Criteria (CTCAE v4). The investigator will determine relationship of toxicity to the investigational drug as unrelated, unlikely related, possibly related, probably related, or definitely related using standard criteria for clinical trials. All grades of toxicity will be noted and reported as directed in Table I: Clinical Data Update System (CDUS) Guidelines for Routine Adverse Event Reporting.

Patients who experience a CTCAE (version 4) Grade 3 or 4 toxicity that is considered related to Vandetanib will have their study drug stopped. If a patient discontinues treatment, safety follow-up visits will be performed according to the schedule of assessments and procedures. In addition, a 30 day follow up visit will occur if AEs have not resolved by the time of the post op safety visit. SAEs and study drug-related AEs must be followed until resolution unless in the Investigator’s opinion, the event is unlikely to resolve due to the patient’s underlying condition.

Cardiac toxicity - QTc prolongation

Electrocardiograms will be evaluated by suitably qualified personnel for the presence of QTc prolongation or other abnormalities, in particular, any changes in the T-wave morphology that would suggest a higher likelihood for the development of any arrhythmia. Any clinically significant abnormal findings or QTc prolongations will be recorded as AEs.

In addition to scheduled ECG, additional ECGs should also be performed in the event of QTc prolongation, both during and post the prolongation period.

- During the QTc prolongation period: For a single QTc value of >500 ms, Vandetanib must be withheld and patients will be removed from the study. Electrocardiograms will be followed at least once per week (done at the same day each week) along with electrolytes, until QTc falls \leq 480 ms.

Gastrointestinal toxicity

Nausea, vomiting, or both may be controlled with anti-emetic therapy. The use of somatostatin or a somatostatin analogue is allowed to control diarrhea.

Diarrhea should be treated with standard medications to avoid dose modification or interruption, if possible. Electrolyte supplementation with regular laboratory monitoring should be used, when appropriate, to maintain electrolytes within normal limits and prevent an increased risk of QTc prolongation.

If CTCAE Grade 3 or 4 diarrhea develops, patients will be removed from the study. Any electrolyte imbalance must be promptly corrected since hypokalemia and hypomagnesaemia are potential risk factors for drug-induced arrhythmia.

Cutaneous toxicity

It is strongly recommended that all patients follow a program of sun protective measures (wearing additional clothing and/or sunscreen) while receiving study treatment and for 3 to 4 weeks after discontinuing study treatment. The aim is to reduce the risk of development of skin rash, or minimize the severity of skin rash, and to minimize the requirement for dose reduction of study therapy.

If a patient develops a skin rash, the following actions are recommended to the Investigator for the management of this reaction:

- A variety of agents can be used to manage skin rashes. These include mild to moderate strength steroid creams or systemic glucocorticoids, either topical or systemic antibiotics, topical or systemic antihistamines, and occasionally retinoid creams.
- The rash should be graded as soon as possible according to the CTCAE cutaneous toxicity criteria.
- If a rash of CTCAE Grade 2 or higher is detected, immediate symptomatic treatment should be provided.
- If a rash of CTCAE Grade 3 or 4 is detected, patients will be removed from the study

Hypertension

Patients who develop CTCAE Grade 3 hypertension may continue on therapy if blood pressure is controlled on increased anti-hypertensive medication (to CTCAE Grade 1 or baseline). If blood pressure cannot be stabilized with increased anti-hypertensive medication, patients will be removed from the study.

Patients with CTCAE Grade 4 hypertension must be removed from the study.

11.2.4 Adverse Event Reporting:

Table I:

Clinical Data Update System (CDUS) Guidelines for Routine Adverse Event Reporting

Attribution	Adverse Event				
	Grade 1	Grade 2	Grade 3	Grade 4	Grade 5
Unrelated	Not required	Not required	CRSO	CRSO	CRSO
Unlikely	Not required	Not required	CRSO	CRSO	CRSO
Possible	CRSO	CRSO	CRSO	CRSO	CRSO
Probable	CRSO	CRSO	CRSO	CRSO	CRSO
Definite	CRSO	CRSO	CRSO	CRSO	CRSO

Reports are collected by the CRSO or DSMB and communicated to the DSMC

For Hospitalization Only — Any medical event equivalent to CTC Grade 3, 4, 5 which precipitated hospitalization (or prolongation of existing hospitalization) must be reported regardless of requirements of Phase of Study, expected or unexpected grade and attribution.

All adverse events related to the experimental procedures will be reported to the Data Safety Monitoring Committee (DSMC) via the Clinical Research Safety Officer (CRSO) as well as the appropriate regulatory authority. Annual progress reports will be sent to the CRO, who will enter this into OnCore and report findings to the DSMC. Only

Grade 4 and 5 events that are unexpected with at least possible attribution to Vandetanib will require an **expedited report**. The investigator will continue to follow or obtain documentation of the resolution course of such an event. The event may also require reporting to the IRB, as determined by current policies (http://research.uiowa.edu/hso/downloads/policies/Guide_Human_Subjects_Research.pdf).

Investigators and other site personnel must inform the FDA, via a MedWatch/AdEERs form, of any serious or unexpected adverse events that occur in accordance with the reporting obligations of 21 CFR 312.32., and will concurrently forward all such reports to AZ. A copy of the MedWatch/AdEERs report must be faxed to AstraZeneca at the time the event is reported to the FDA. It is the responsibility of the investigator to compile all necessary information and ensure that the FDA receives a report according to the FDA reporting requirement timelines and to ensure that these reports are also submitted to AstraZeneca at the same time.

When reporting to AstraZeneca, a cover page should accompany the MedWatch/AdEERs form indicating the following:

- Investigator Sponsored Study (ISS)
- The investigator IND number assigned by the FDA
- The investigator's name and address
- The trial name/title and AstraZeneca ISS reference number (#ISS64740032)

Investigative site must also indicate, either in the SAE report or the cover page, the causality of events in relation to all study medications and if the SAE is related to disease progression, as determined by the principal investigator.

Send SAE report and accompanying cover page by way of fax to AstraZeneca's designated fax line: [name]

Serious adverse events that do not require expedited reporting to the FDA need to be reported to AstraZeneca preferably using the MedDRA coding language for serious adverse events.

In the case of blinded trials, AstraZeneca will request that the Sponsor either provide a copy of the randomization code/ code break information or unblind those SAEs which require expedited reporting.

All SAEs have to be reported to AstraZeneca, whether or not considered causally related to the investigational product. All SAEs will be documented. The investigator is responsible for informing the IRB and/or the Regulatory Authority of the SAE as per local requirements.

Overdose

If an overdose on an AstraZeneca study drug occurs in the course of the study, then investigators or other site personnel inform appropriate AstraZeneca representatives **within one day**, i.e., immediately but no later than **the end of the next business day** of when he or she becomes aware of it.

The designated AstraZeneca representative works with the investigator to ensure that all relevant information is provided to the AstraZeneca Patient Safety data entry site.

Pregnancy

All outcomes of pregnancy should be reported to AstraZeneca.

Maternal exposure

Pregnancy itself is not regarded as an adverse event unless there is a suspicion that the investigational product under study may have interfered with the effectiveness of a contraceptive medication. However, the outcome of all pregnancies (spontaneous miscarriage, elective termination, normal birth or congenital abnormality) must be followed up and documented even if the subject was discontinued from the study. Should pregnancy occur during a female subject's trial participation, the female subject will immediately be discontinued from the trial and followed-up.

All reports of congenital abnormalities/birth defects are SAEs. Spontaneous miscarriages should also be reported and handled as SAEs. Elective abortions without complications should not be handled as AEs. All outcomes of pregnancy must be followed-up, documented and reported to AstraZeneca. The following information must be reported to AstraZeneca:

- DOB, Occupation
- Relevant medical history (pregnancy risk factors, smoking alcohol, etc.)
- Relevant family history
- Previous pregnancies (overall number, deliveries, spontaneous miscarriage, etc)
- Current pregnancy (LMP, expected delivery date, any amniocentesis, chorionic villus sampling, in-vitro fertilization)
- Concomitant medications taken during pregnancy (name, total daily dose, therapy duration, indication)
- Outcome of pregnancy (i.e., full-term, premature birth, spontaneous miscarriage, elective termination. If premature birth, specify gestational age in weeks. If elective abortion, specify if any medical reason.)
- Details of birth (i.e., DOB, weight, sex, healthy baby, sick baby, congenital anomaly/birth defect, still birth, multiple births, sickness manifestations, etc.)
- Any complications, infections, illness during pregnancy

The most common side effects seen in patients treated with Vandetanib included the following:

Risks for Vandetanib

Very Common (experienced by more than 10% of patients taking Vandetanib)

Headache
Diarrhea
Nausea/vomiting
Constipation
Decreased appetite,
Rash
Dry skin
Hypertension
Trouble sleeping
Weakness
Fatigue

Common (Experienced by 1 – 10% of patients taking Vandetanib)

QTc prolongation
Abnormal taste in mouth
Abdominal pain
Mouth swelling
Dry mouth
Weight loss
Elevated liver function tests
Anorexia
Hypokalemia
Hypocalcemia
Dehydration
Hypomagnesemia
Skin changes
Acne
Hair loss
Nail disorders
Mild nose bleed
Proteinuria
Kidney stone
Visual problems
Depression
Anxiety

Uncommon (Experienced by fewer than 1% of patients taking vandetanib)

Heart failure
Chest pain
Pancreatitis
Thrombocytopenia
Severe skin disorder
Seizure
Shortness of breath
Hypokalemia

